## **6.6. Sample Handling**

To minimise variability between centres in this multicentre study all clinical laboratory assays will be performed by a central laboratory (see details on Study Contacts Section). Blood samples are to be handled, shipped and stored according to the instructions provided by the laboratory. Laboratory kits, shipment material and a comprehensive laboratory manual will be provided to all sites.

Instructions for handling, shipment and storing of blood and urine samples for Biomarkers testing will be described in a separate laboratory manual.

Samples for future Biomedical Research of those patients providing consent, will be appropriately stored in the central laboratory facilities. Details will be included in the laboratory manual.

## **6.7. PK Samples**

### **Blood Sampling FAB122**

Blood sampling for FAB122 PK analysis will be done in ~90 subjects in selected sites. Of those ~30 subjects will participate in a PK profiling sampling schedule and the additional ~60 subjects will participate in a population PK sampling schedule, both at baseline, week 4 and week 48 (or Early Termination).

Sampling schedule for PK profiling: pre-dose and 15 min, 30 min, 1, 1.5, 2, 4 hrs., and 6hrs. after the FAB122 morning dose. The pre-dose sample may be collected within 30 minutes prior to dosing. 15 and 30 min post dosing samples should be taken within  $\pm 2$  minutes of the scheduled time, the 1 hr. post dosing sample within  $\pm 5$  minutes, the 1.5 and 2-hour sample within  $\pm 10$  minutes and the 4 hr. and 6hr. sample within  $\pm 20$  minutes of the scheduled time. The time of sampling will be accurately recorded.

Sampling schedule for population PK: (1) pre-dose (within 1 hour prior to dosing), (2) within 5- and 30-minutes post dosing, (3) 1 hour and (4) 1.5 hour after the second PK sample was taken. The time of sampling will be accurately recorded.

Patient should come fasted and will take the IMP dose in the clinic.

Patients participating in the PK profiling will not be allowed to eat until 4 hours post dose.

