9. Blood sampling for FAB122 PK analysis will be done in ~90 subjects in selected sites. Of those ~30 subjects will participate in a PK profiling sampling schedule and the additional ~60 subjects will participate in a population PK sampling schedule. Sampling schedule for PK profiling: pre-dose and 15 min, 30 min, 1, 1.5, 2, 4 hrs., and 6hrs, after the FAB122 morning dose. The pre-dose sample may be collected within 30 minutes prior to dosing, the samples taken 15 and, 30 min post dosing samples should be taken within ±2 minutes of the scheduled time, the 1 hr. post dosing sample within ±5 minutes, the 2-hour sample within ±10 minutes and the 4 hr. and 6hr. sample within ±20 minutes of the scheduled time. The time of sampling will be accurately recorded. Sampling schedule for population PK: (1) pre-dose (within 1 hour prior to dosing), (2) within 5- and 30-minutes post dosing, (3) 1 hour and (4) 1.5 hour after the second PK sample was taken.

10. Blood sampling for the determination of riluzole concentration will be done in the subjects included in FAB122 population PK sampling in baseline and week 4 (~90 subjects) at (1) pre-dose (within 1 hour prior to dosing), (2) within 5- and 30-minutes post dosing, (3) 1 hour and (4) 1.5 hour after the second PK sample was taken. In case of discontinuation of a subject, due to safety reasons or early termination of the study, a PK sample for determination of the FAB122 concentration is to be taken in those sites where FAB122 sampling is operational. The clock time and time after last dosing is to be noted in the CRF.

11. Blood biomarkers: neurofilament, light chain (NFL). Serum creatinine and serum creatine kinase will be measured in biochemistry lab testing.

12. Urine biomarkers: 8-hydroxy-2'-deoxyguanosine (8-OhdG), extracellular domain of neurotrophin receptor p75 (p75ECD).

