#### 6.5. Early Discontinuation/Withdrawal of Participants

Subjects may withdraw consent at any time for any reason or be dropped from the trial at the discretion of the investigator should any untoward effect occur. In addition, a subject may be withdrawn by the investigator or the Sponsor if enrolment into the trial is inappropriate, the trial plan is violated, or for administrative and/or safety reasons.

In this trial, a subject may discontinue from treatment but continue to participate in the regularly scheduled activities, as long as the subject does not withdraw consent. Once a subject has discontinued treatment, he/she may be allowed to start treatment again after consultation with the investigator, if discontinuation of treatment is  $\leq$  2 weeks.

A subject must be discontinued from the trial for any of the following reasons:

- The subject withdraws consent.
- The subject has a medical condition or personal circumstances which, in the opinion of the investigator and/or Sponsor, places the subject at unnecessary risk if participation in the trial is continued.
- The subject reaches the criteria for respiratory insufficiency (tracheostomy or the use of non-invasive ventilation for >20 hours per day for >10 consecutive days),

A subject must be discontinued from study treatment (but should continue to be monitored in the study) for any of the following reasons:

1-The subject becomes pregnant during the study.

2-The subject's investigator considers it is in the best interest of the subject to discontinue including worsening or disease progression if the investigator considers that it is in the patient's best interest the initiation of any standard of care treatment prohibited in the study

3-Serious adverse event considered related to the IMP

4-Severe Neurotoxicity considered related to the IMP

5-Any other severe adverse event considered related to the IMP at the discretion of the investigator.

6-Acute renal failure (creatinine clearance of less than 30 mL/min as calculated by the Cockcroft Gault equation)

7-Severe liver disorder defined as:

- ALT/AST  $\geq$  3xULN and bilirubin  $\geq$  2xULN ( $>35\%$  direct bilirubin)
- ALT/AST  $\geq$  8xULN
- ALT/AST  $\geq$  3xULN and with symptoms believed to be related to liver injury or hypersensitivity.
- ALT/AST  $\geq$  3x baseline ALT/AST and with symptoms believed to be related to liver injury or hypersensitivity.

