- ALT/AST  $\geq$  5xULN and ALT/AST  $<$  8xULN that persists more than two weeks

8-Acute lung injury with pyrexia, cough, dyspnoea and chest X-ray abnormality

9-Rhabdomyolysis

10-Disseminated intravascular coagulation (DIC)

11-Hypersensitivity reaction

12- Anaphylactic reaction/shock

13- Thrombocytopenia

14- Neutropenia

15-Introduction of riluzole

16-The subject cannot attend two consecutive study visits and key safety assessment cannot be performed

If a subject discontinues the trial for safety reasons, a PK sample is to be taken (with the time of sampling after last dosing clearly documented) in those sites participating in the PK sub study.

In case a subject withdraws FBR consent, the blood samples taken for FBR will be destroyed (when not analysed yet).

The sponsor reserves the right to terminate the study at any time if continuation of the protocol would present a potential safety risk to the subjects.

Every effort will be made to ensure that patients who do not complete all study requirements return to the site for the End-of-Trial Visit. Patients who withdraw due to an Adverse Event (AE) or Serious Adverse Event (SAE) will be given appropriate care under medical supervision until the symptoms resolve or the patient's condition becomes stable. The End-of-Trial Visit will be performed 7-14 days after withdrawal and the same procedures as Visit 8 will be performed.

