**Table 3: Overview of PK sampling**

Baseline (V1)	Week 4 (V2)	Week 48 (V6)*	Early Termination**
30 subjects FAB122 PK profiling Riluzole PK*** pre-dose and 0.25, 0.5, 1, 1.5, 2, 4 hrs., and 6hrs after FAB122/riluzole morning dose	30 subjects FAB122 PK profiling Riluzole PK*** pre-dose and 0.25, 0.5, 1, 1.5, 2, 4 hrs., and 6hrs after FAB122/riluzole morning dose	30 subjects FAB122 PK profiling Riluzole PK*** pre-dose and 0.25, 0.5, 1, 1.5, 2, 4 hrs., and 6hrs after FAB122 morning dose	30 subjects FAB122 PK profiling Riluzole PK*** pre-dose and 0.25, 0.5, 1, 1.5, 2, 4 hrs., and 6hrs after FAB122 morning dose
60 subjects FAB122 PK population Riluzole PK pre-dose (within 1 hour prior to dosing), (2) within 5- and 30- minutes post dosing, and (3) 1 hour and (4) 1.5 hour after the second PK sample was taken	60 subjects FAB122 PK population Riluzole PK pre-dose (within 1 hour prior to dosing), (2) within 5- and 30- minutes post dosing, and (3) 1 hour and (4) 1.5 hour after the second PK sample was taken	60 subjects FAB122 PK population Riluzole PK pre-dose (within 1 hour prior to dosing), (2) within 5- and 30- minutes post dosing, and (3) 1 hour and (4) 1.5h after the second PK sample was taken	60 subjects FAB122 PK population Riluzole PK pre-dose (within 1 hour prior to dosing), (2) within 5- and 30- minutes post dosing, and (3) 1 hour and (4) 1.5h after the second PK sample was taken

\*If feasible (if patients continue up to week 48)

\*\*Only for patients included in the FAB122 profiling PK and FAB122 population PK and who discontinue treatment before week 48

\*\*\*Riluzole will only be analyzed in pre-dose, 0.5, 1.5 and 2h samples.

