#### **9.9.      Pregnancy**

If a patient becomes pregnant during the study or within the safety follow-up period defined in the protocol, the Investigator is to stop dosing with study drug(s) immediately and the patient should be withdrawn from the study. Early termination procedures should be implemented at that time.

A pregnancy as such is not an AE, however, it must be reported to the Sponsor within 24 hours of knowledge of the event completing a Pregnancy Reporting Form.

Female patients will be instructed to notify the investigator immediately if they become pregnant during the study. Male patients will be instructed to notify the investigator immediately if their partner becomes pregnant. Pregnant patients will be withdrawn from further study treatment. The patients will also be instructed to report pregnancies discovered after the last visit, if they believe that conception occurred during their participation in the study.

The pregnant patient or partner will be followed until the end of the pregnancy. Any complication during the pregnancy should preferably be reported as an AE. The outcome of the pregnancy must be reported on the Pregnancy Reporting Form. Any spontaneous abortion, stillbirth, birth defect/congenital anomaly, death, or other serious infant condition must be reported and followed up as an SAE. If the pregnancy outcome meets seriousness criteria the both the SAE form and pregnancy form should be forwarded.

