10. Blood sampling for the determination of riluzole concentration will be done in the subjects included in FAB122 population PK sampling in baseline and week 4 (~90 subjects) at (1) pre-dose (within 1 hour prior to dosing), (2) within 5- and 30-minutes post dosing, (3) 1 hour and (4) 1.5 hour after the second PK sample was taken. In case of discontinuation of a subject, due to safety reasons or early termination of the study, a PK sample for determination of the FAB122 concentration is to be taken in those sites where FAB122 sampling is operational. The clock time and time after last dosing is to be noted in the CRF.
11. Blood biomarkers: neurofilament light chain (NFL). Serum creatinine and serum creatine kinase will be measured in biochemistry lab testing.
12. Urine biomarkers: 8-hydroxy-2'-deoxyguanosine (8-OhdG), extracellular domain of neurotrophin receptor p75 (p75ECD).
13. Optional CSF sampling will be performed (if consented) in about 30 patients at baseline, week 12, and week 24. Lumbar Puncture for CSF sampling is an aseptic procedure which needs standard bedside aseptic procedures with no-touch technique, sterile drapes and use of chlorhexidine or an equivalent antiseptic. Local anaesthesia with small amount of lidocaine can be infiltrated. A right-handed practitioner should position the patient in the left lateral decubitus position, with the vertebrae in line with the horizontal plane and the head in a neutral position and the knees flexed, also setting position could be applied if seemed by the practitioner. The bony landmark is the L4 spinous process and the L3/L4 interspace is recommended. Atraumatic 22-gauge needle could be used, however smallest diameter needle with which the practitioner can confidently perform the procedure avoiding an increased number of attempts should be chosen. 10 ml CSF sample will be drawn at each time point. After the procedure, a small sterile dressing is placed on the site and the patient can mobilise as soon as it is comfortable to do so. Regular analgesics such as paracetamol could be prescribed.
14. Only labs parameters that are abnormal in the screening visit will be re-evaluated in baseline visit.

\* In case it's necessary, NCS assessment can be performed during the baseline visit, provided the approval from the central reader are available prior to randomization.

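### Section 6.7 and Table 3 call for PK sampling around a new FAB122 dose at Early Termination without exempting patients whose drug must be stopped, and the single safety-stop sample has no time limit

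*Protocol*

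**What the plan says.** Protocol section 6.7 (Blood Sampling FAB122) places the profiling and population PK schedules "both at baseline, week 4 and week 48 (or Early Termination". The dosing instruction that follows, "Patient should come fasted and will take the IMP dose in the clinic", names no visit and no exception. Table 3 has a separate Early Termination column with pre-dose and post-dose samples. Its footnote says whom the column is for: "Only for patients included in the FAB122 profiling PK and FAB122 population PK and who discontinue treatment before week 48". No reason for stopping is excluded.

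Section 6.5 gives the mandatory stops: "A subject must be discontinued from study treatment (but should continue to be monitored in the study) for any of the following reasons". The list includes related serious adverse events, severe neurotoxicity, severe liver disorder, hypersensitivity, anaphylaxis and pregnancy. For pregnancy, section 9.9 adds that "the Investigator is to stop dosing with study drug(s) immediately", and it calls for early termination procedures at the same time.

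Three other places ask for one sample only. Section 6.5 says "If a subject discontinues the trial for safety reasons, a PK sample is to be taken" and wants the interval since the last dose documented. The Table 1 footnotes say that on discontinuation for safety or early termination "a PK sample for determination of the FAB122 concentration is to be taken in those sites where FAB122 sampling is operational". SAP section 2.5 repeats the footnote: "In case of discontinuation of a subject, due to safety reasons or early termination of the study, a PK sample". Both footnotes ask for the clock time and the time since the last dose. None of the three gives a deadline. Among the visit lists in section 6.3, only Visit 8/End of Trial carries an early-withdrawal FAB122 sample.

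**The concern.** Two instructions cover the same patient and disagree. If a PK sub-study patient must stop FAB122, for example after a related serious adverse event, Table 3 read on its own asks the site to give another dose and sample around it. Section 6.5 says the drug must stop, and the footnotes ask for a single sample with no dose. Table 3 does not refer to section 6.5, so staff working from the PK table would not be pointed to the stop rule. What is at stake is re-exposure of a patient after a mandatory stop.

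The second issue is what the single sample can show. Its use is to record exposure close to the event. With no time limit, a site that works from the visit lists would draw it at the End-of-Trial visit, which for a patient leaving the trial is a week or more after withdrawal. The protocol describes neurological toxicity in animals at relatively low safety margins, makes suspected neuropathy an event of special interest, and foresees exposure-response work. An informative concentration near such an event is therefore worth having.

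**Working it through.** **The conflict in the text.** The documents give no figure to reproduce here, so the instructions are set side by side.

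| Source | Visit or trigger | New dose | FAB122 samples |
|---|---|---|---|
| Section 6.7 and Table 3, profiling group | Early Termination, treatment stopped before week 48 | Yes | 1 pre-dose + 7 post-dose (0.25, 0.5, 1, 1.5, 2, 4, 6 h) = 8 |
| Section 6.7 and Table 3, population PK group | Same | Yes | 1 pre-dose + 3 post-dose = 4 |
| Section 6.5; Table 1 footnotes; SAP 2.5 | Discontinuation for safety; footnotes also early termination | None stated; timed from last dose | 1 |
| Section 6.3, Visit 8 | Early withdrawal | No dosing step listed | Sampling listed, number not given |

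Section 8.3.1 gives the schedules at baseline, week 4 and week 48 only, and the SAP schedule marks the FAB122 sample at the last visit differently from those three. So section 6.7 and Table 3 are the outliers. The restart option in section 6.5, for pauses of up to 2 weeks, is not linked to PK sampling and does not resolve the conflict.

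**How many patients.** Section 11.4 expects about 7% adverse-event stops in the experimental arm. Section 4 speaks of about 90 PK patients treated with study drug. Section 8.3.1, however, plans a comparison with riluzole-plus-placebo patients, which at 2:1 would leave 90 x 2/3 = 60 on FAB122. The denominator is therefore assumed to be 60 to 90:

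- 0.07 x 60 = 4.2
- 0.07 x 90 = 6.3

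This is an upper figure for adverse-event stops, because not every such stop is on the mandatory list. The documents give no rate for other mandatory stops such as pregnancy.

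**How much drug is left.** The protocol's half-life is about 5 h (section 2.1). Fraction left after the last dose = 0.5^(hours / half-life):

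- 12 h: 0.5^2.4 = 0.19
- 24 h: 0.5^4.8 = 0.036
- 48 h: 0.5^9.6 = 0.0013
- 7 days (168 h): 0.5^33.6 = 7.7e-11
- 14 days (336 h): 0.5^67.2 = 5.9e-21

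With the half-life varied from 3 to 10 h as an assumption, the fraction at 24 h runs from 0.4% to 19%, and at 7 days from 1.4e-17 to 8.8e-6. The conclusion for day 7 does not depend on the exact half-life.

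**Which window applies to whom.** Section 6.5 puts the End-of-Trial visit 7-14 days after withdrawal, and SAP section 2.5, note 2, puts it 7-14 days after study termination in case of withdrawal or early termination. The same note gives 1-14 days after treatment cessation for patients not entering the extension. Note 1 asks patients who only stop treatment to return for End-of-Trial procedures and states no delay. The day-7 result therefore applies to patients who leave the trial and are sampled from the Visit 8 list. Under the 1-14 day window, a day-1 sample would hold about 3.6%.

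**The case against.** The best reply is that the documents already bar re-dosing. Section 6.5 is mandatory, section 9.9 stops dosing at once in pregnancy, and the single-sample rule is written for safety discontinuations and presupposes no new dose. A sampling overview does not override a stop rule. Table 3's Early Termination column can also be followed without conflict by patients who stop voluntarily. All of this stands. A reader might infer that the protocol directs sites to re-dose after anaphylaxis; the documents do not support that, because the mandatory rule should prevail. What remains is that section 6.7 and Table 3 state a procedure that is wrong for these patients and do not point to the rule that displaces it.

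On timing, the reply is that the single sample is triggered by the discontinuation and not tied to a visit, so a site may draw it on the day the drug stops. That also stands. A reader might infer that every safety-stop sample comes too late to be useful. The text does not support this: patients who stop treatment but remain in follow-up have no stated delay or fall under the 1-14 day window, and a day-1 sample may be measurable. The gap is the absence of any time limit, together with a visit list that leads some sites to a late draw.

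It is also fair that the numbers are small and that baseline and week 4 samples still describe usual exposure.

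**Conclusion.** The point holds as a conflict in the safety and PK instructions and should be corrected. Section 6.7 and Table 3 call for a new in-clinic dose and 8 or 4 samples at Early Termination, with no exemption for mandatory stops under section 6.5 or 9.9. They disagree with the single sample timed from the last dose. The exposed group is small: at most about 4 to 6 adverse-event stops, resting on the expected 7% rate and an assumed 60 to 90 treated PK patients, plus an unknown number of other mandatory stops. Fewer still would actually be re-dosed, since the stop rules should be followed.

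The timing part is narrower. For patients who leave the trial and are sampled at End of Trial, essentially nothing remains (about 8e-11 at day 7 with a 5 h half-life). For others the sample may be drawn earlier, but nothing requires it. A reader should not carry this over to the efficacy results: the primary and key secondary endpoints are unaffected.

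**What to change.** In section 6.7 and under Table 3, state that patients whose IMP is stopped under the mandatory list in section 6.5, or under section 9.9, receive no further IMP and have no post-dose sampling at Early Termination.

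In section 6.5 and the Table 1 footnote, with its copy in SAP section 2.5, require one undosed PK sample as early as feasible after the event or the decision to stop. The clock time and the time of the last dose should be recorded, and the sample should not be deferred to the End-of-Trial visit.

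The cost is a wording change. Affected patients have 1 draw instead of 4 or 8. The downside is that safety stops yield no post-dose profile, and patients who cannot attend promptly may yield no informative sample. Patients who stop for reasons outside those rules are not touched by the change.

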**Blood Sampling Riluzole**

Blood sampling for the determination of riluzole concentration will be done in the subjects included in FAB122 PK sampling in baseline and week 4 (~90 subjects) at (1) pre-dose (within 1 hour prior to dosing).(2) within 5- and 30-minutes post dosing, (3) 1 hour and (4) 1.5 hour after the second PK sample was taken. The time of sampling will be accurately recorded.

Patient should come fasted and will take the riluzole dose in the clinic, at the same time that the IMP dose.

**Table 3: Overview of PK sampling**

Baseline (V1)	Week 4 (V2)	Week 48 (V6)*	Early Termination**
30 subjects FAB122 PK profiling Riluzole PK*** pre-dose and 0.25, 0.5, 1, 1.5, 2, 4 hrs., and 6hrs after FAB122/riluzole morning dose	30 subjects FAB122 PK profiling Riluzole PK*** pre-dose and 0.25, 0.5, 1, 1.5, 2, 4 hrs., and 6hrs after FAB122/riluzole morning dose	30 subjects FAB122 PK profiling Riluzole PK*** pre-dose and 0.25, 0.5, 1, 1.5, 2, 4 hrs., and 6hrs after FAB122 morning dose	30 subjects FAB122 PK profiling Riluzole PK*** pre-dose and 0.25, 0.5, 1, 1.5, 2, 4 hrs., and 6hrs after FAB122 morning dose
60 subjects FAB122 PK population Riluzole PK pre-dose (within 1 hour prior to dosing), (2) within 5- and 30- minutes post dosing, and (3) 1 hour and (4) 1.5 hour after the second PK sample was taken	60 subjects FAB122 PK population Riluzole PK pre-dose (within 1 hour prior to dosing), (2) within 5- and 30- minutes post dosing, and (3) 1 hour and (4) 1.5 hour after the second PK sample was taken	60 subjects FAB122 PK population Riluzole PK pre-dose (within 1 hour prior to dosing), (2) within 5- and 30- minutes post dosing, and (3) 1 hour and (4) 1.5h after the second PK sample was taken	60 subjects FAB122 PK population Riluzole PK pre-dose (within 1 hour prior to dosing), (2) within 5- and 30- minutes post dosing, and (3) 1 hour and (4) 1.5h after the second PK sample was taken

\*If feasible (if patients continue up to week 48)

\*\*Only for patients included in the FAB122 profiling PK and FAB122 population PK and who discontinue treatment before week 48

\*\*\*Riluzole will only be analyzed in pre-dose, 0.5, 1.5 and 2h samples.

